Sweet consumption and subsequent sweet food preferences and intakes:

Protocol

Study ID number: NCT05672017

Document date: 31.05.25.

Design

This study utilised a parallel-groups, randomised controlled trial design with three arms. Participants were randomised to either increase, decrease or make no change to their daily intake of sweet-tasting foods and beverages for 6 consecutive days. All outcomes were assessed at two time points, on day 0 (baseline) and day 7 (end), alongside measures of adherence to the assigned diet.

Participants

A priori power calculations were based on changes in pleasantness ratings of approximately 6–9 mm (SD = approx. 13–17 mm), as reported in response to sweet taste exposure over 6 d in two previous studies(12,17) . For a two-sided α of 0·05 and power of 0·8, these calculations estimated the need for forty participants per intervention group. Eligibility criteria for the study were being over the age of 18 years, non-vegan and non-smoker, regularly consuming breakfast, having no food allergies, not pregnant or breastfeeding, not dieting or trying to lose weight and being willing and able to undertake all study requirements.

Participants were recruited using personal contacts, posters and online advertisements and through internal research volunteering platforms. To conceal our specific interest in sweet foods, the trial was described as a study of 'Eating Behaviours' with candidates advised that they would be required to modify specific aspects of their diet as instructed, although details of the modification were not given at this stage. In advance of participation, all interested candidates received study information and consent documents, and all participants provided written informed consent. The trial was designed and conducted according to the guidelines laid down in the Declaration of Helsinki (1983), the Ethical Guidelines of the British Psychological Society and the Research Ethics Codes of Practice of Bournemouth University, UK, and the University of Bristol, UK. All procedures involving human participants were approved by the Research Ethics Committees of Bournemouth University (ID: 47051/48807/45568) and the University of Bristol (ID: 06121760961) prior to commencement. Risk assessments were carried out before data collection, with regular reviews undertaken throughout the trial and all risks addressed accordingly.

Intervention/control

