that are experienced as tasting sweet v. not sweet by each individual. For those in the control arm, no dietary change was required. Participants were simply asked to 'Continue consuming all foods and drinks that you were consuming last week'. Intervention instruction guides were provided to participants in written form for them to take away and refer to as they wished. In addition, on receipt of their instructions, participants were reminded that the aim of the study (as disclosed during consent procedures) was to investigate the effects of a dietary change and were asked to make this change as substantial as possible to enhance our chances of finding effects. The researcher in contact with participants was not aware of the specific instructions given, but contact details of an additional researcher were also given should questions arise during the course of the study. Participants were asked to undertake the intervention for 6 d (days 1–6) with outcomes assessed on day 0 and day 7.

Outcomes

Our primary outcomes were pleasantness and desire to eat for sweet and non-sweet foods and sweet food intake assessed at an ad libitum cold, buffet-style, breakfast meal.

Secondary outcomes were perceived sweet taste intensity of the sweet and non-sweet foods, self-reported adherence to the allocated diet and measures of appetite.

Pleasantness and desire to eat

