Adherence to the intervention instructions was assessed at the end of the intervention period. Participants were asked how well they adhered to their allocated diet ('How well did you adhere (manage to keep) to your allocated diet?', response anchors: 'not at all', 'extremely'), how difficult they found it to adhere to their allocated diet ('How difficult did you find it to adhere (manage to keep) to your allocated diet?', response anchors: 'not at all', 'extremely') and how different their allocated diet was from their usual diet ('How different was your allocated diet from your usual diet?', response anchors: 'not at all', 'extremely'). Responses were made using paper and pen 100 mm visual analogue scales and were verified using records of sweet food consumption over the previous day and verbal reports of difficulties over the intervention week.

Appetite

Ratings of hunger, fullness and thirst were also undertaken using paper and pen 100 mm visual analogue scales at the start of each test session to allow for differences in appetite on each test day. Participant age and sex were also collected for descriptive purposes.

Procedure

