The study was run from both the University of Bristol, UK (February 2018–May 2018), and from Bournemouth University (January 2023–May 2023, October 2023–March 2024). The initial study began at the University of Bristol and, following disruptions due to COVID-19, was continued later at Bournemouth University. Data collection was carried out at the Nutrition and Behaviour Unit at the University of Bristol and the Eating Behaviours Laboratory at Bournemouth University. Participants visited the testing site fasted and rested on day 0 and day 7 during pre-booked time slots. Visits were scheduled between 08.00 and 11.00, and the timeslots remained the same on both occasions. Upon arrival, participants were seated individually at a table where they were presented with the taste perception test. After completing this test, participants received their cold buffet-style breakfast. The entire procedure lasted approximately 30 min and was repeated exactly on both testing occasions, with three exceptions. At the end of day 0 following all data collection, participants were provided with their dietary intervention. On day 7, participants also completed the adherence questions before the taste perception test, and they were asked about any difficulties experienced over the intervention period. After their breakfast, they were also debriefed about the purpose of the research and thanked for participating in the study. To maintain a researcher-blinded study design, an independent researcher with no contact with participants randomised participants to one of the trial arms using a random number generator. Participants were randomised at a ratio of 1 (increase): 1 (decrease) at the University of Bristol and subsequently at a ratio of 1 (increase): 1 (decrease): 1 (no change) at Bournemouth University, to result in a final sample with a ratio of 2 (increase): 2 (decrease): 1 (no change). Group allocation was concealed using white sealed, opaque envelopes, and throughout the trial, the researcher in direct contact with participants remained unaware of each participant's group allocation. To support the blinding,

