Hunger and thirst will be assessed using self-report ratings of 'How HUNGRY are you right now?', response anchors: 'not at all', 'extremely'; 'How FULL are you right now?', response anchors: 'not at all', 'extremely'; and 'How THIRSTY are you right now?', response anchors: 'not at all', 'extremely'; using 100 mm visual analogue scales (VAS). Data are provided in mm from 0 to 100mm.

Compliance

Compliance with the intervention instructions will also be assessed at the end of the intervention period. Participants will be asked how well they adhered to the allocated diet ('How well did you adhere (manage to keep) to your allocated diet?', response anchors: 'not at all', 'extremely'), how difficult they found it to adhere to the allocated diet ('How difficult did you find it to adhere (manage to keep) to your allocated diet?', response anchors: 'not at all', 'extremely') and how different their allocated diet was from their usual diet ('How different was your allocated diet from your usual diet?', response anchors: 'not at all', 'extremely').

Responses will again be made using 100 mm VAS scales. Data will again be provided as mm from 0 to 100mm.

Analyses

Data for all outcome measures will be processed and collated using Microsoft Excel by one researcher who will remain blind to participant condition until all data have been checked and are confirmed.

Following unblinding, data will first be described, by participant group.

Prior to all analyses, data will be checked for normality and other violations of parametric assumptions. Violations will be addressed using corrections, e.g. Greenhouse Geisser, transformations or non-parametric tests will be used where appropriate.

For the taste perception measures, ratings for pleasantness, desire to eat and sweet taste intensity will be averaged across all sweet and non-sweet foods tested, resulting in two scores per outcome measure, one for sweet and one for non-sweet foods. These will then be analysed using 3 condition (increase sweet food consumption, decrease sweet food consumption, no diet change) x 2 time (day 0, day 7) x 2 food type (sweet foods, non-sweet foods) repeated-measures ANOVAs.

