For sweet food intake measures, the weight of foods consumed in grams, will be calculated by subtracting the weight of foods returned to the kitchen from the amount served at breakfast, and used to calculate the percentage weight consumed from sweet foods and the percentage weight consumed from sweet foods and beverages. Manufacturer's information will then be used to calculate the percentage of energy consumed from sweet foods, percentage energy consumed from sweet foods and beverages, the weight of sugar consumed from foods, the weight of sugar consumed from sweet foods and beverages, the percentage of energy consumed from sugar from foods, and the percentage energy consumed from sugar from foods and beverages. Intake will then be analysed using 3 condition (increase sweet food consumption, decrease sweet food consumption, no diet change) x 2 time (day 0, day 7) repeated-measures ANOVAs.

Appetite will be assessed using 3 condition (increase sweet food consumption, decrease sweet food consumption, no diet change) x 2 time (day 0, day 7) repeated-measures ANOVAs, for each of the three measures.

Compliance will be assessed using 3 condition (increase sweet food consumption, decrease sweet food consumption, no diet change) x 2 time (day 0, day 7) repeated-measures ANOVAs.

Correlations between measures in the taste perception test and the subsequent intake measure will also be conducted.

Analyses will be undertaken on an intention-to-treat basis, with missing data imputed using models based on gender, age and baseline data. Per-protocol analyses may also be undertaken dependent on participant drop out and self-reported compliance.

Analyses will be conducted in SPSS (version 28.0.0.0) or Stata (version 15), as required. Data will be presented as means and standard deviations. Significance will be set at $p = 0.05$.

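### The SAP analyses compliance as a day 0/day 7 repeated measure, but compliance is rated only on day 7 (minor)

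*SAP*

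**What the plan says.** The SAP, in Analyses, specifies: "Compliance will be assessed using 3 condition (increase sweet food consumption, decrease sweet food consumption, no diet change) x 2 time (day 0, day 7"), as repeated-measures ANOVAs. The factor structure is the same as for appetite in the sentence before it.

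On timing, the SAP's Compliance section says: "Compliance with the intervention instructions will also be assessed at the end of the intervention period". The Protocol's Adherence section agrees: "Adherence to the intervention instructions was assessed at the end of the intervention period". The Protocol's Procedure section describes the two visits as the same apart from three listed differences. Two of these matter here: "At the end of day 0 following all data collection, participants were provided with their dietary intervention" and "On day 7, participants also completed the adherence questions before the taste perception test".

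The Protocol's Outcomes section includes among the secondary outcomes "self-reported adherence to the allocated diet and measures of appetite".

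**The concern.** The planned model needs a rating from each participant on both days. Each of the three scales asks about the assigned diet: how well the participant kept to it, how hard that was, and how far it departed from their habitual diet. A participant who has not yet been given a diet cannot answer any of them. If there is no day 0 rating, the stated analysis of a listed secondary outcome cannot be run, and whatever is reported will depart from the SAP. Adherence shows whether the arms followed their instructions and experienced the diets as different, so its prespecified test should be one that can be carried out.

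**Working it through.** There is no stated figure to reproduce. The check is whether a day 0 value exists, and then which terms of the model can be estimated.

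**1. Is there a day 0 value?**

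| Source | What it implies for day 0 |
|---|---|
| SAP, Compliance | Rating placed at the end of the intervention |
| Protocol, Adherence | Same |
| Protocol, Procedure (differences between visits) | Adherence questions added on day 7 |
| Protocol, Procedure (handing out the diet) | Diet unknown to participants until day 0 data are complete |
| Wording of the three scales | All refer to the assigned diet |

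A day 0 rating was neither scheduled nor meaningful.

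**2. What can be estimated?** The 3 x 2 model has an intercept (1), condition (2), time (1) and condition x time (2), so 1 + 2 + 1 + 2 = 6 parameters.

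- With rows at both days, the design matrix has rank 6. Every term is estimable.
- With day 7 rows only, the time column is constant and cannot be separated from the intercept (1 lost). The two interaction columns cannot be separated from the two condition columns (2 lost). The rank is 6 - 1 - 2 = 3, which a numerical rank calculation confirmed. The rank does not depend on group sizes.

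Of the 2 + 1 + 2 = 5 effect degrees of freedom, 3 (time 1, condition x time 2) have no data behind them. The other 2 carry the differences between conditions on day 7. They do not estimate a condition effect averaged over two days.

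**3. What remains?** For each scale, a one-way comparison with 2 and N - 3 df. Purely for illustration, N = 100 (40/40/20, from the 2:2:1 ratio and forty in each of the larger arms) gives 2 and 97 df. N = 120 (forty in each of three arms) gives 2 and 117.

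**4. Does dropping time lose anything?** Suppose the same constant c were entered as everyone's day 0 score. The condition x time F in a two-occasion design is the one-way F on the individual changes, y - c. Subtracting a constant alters neither the between-group nor the within-group sum of squares, so this F equals the one-way F on the day 7 scores y, whatever c is. The time F would only reflect the choice of c. The one-way comparison therefore already holds all the information on condition that the data contain.

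**The case against.** There is text on the other side. The Protocol's Design section says: "All outcomes were assessed at two time points, on day 0 (baseline) and day 7 (end), alongside measures of adherence to the assigned diet". Adherence is listed as a secondary outcome, so a literal reader could take this to mean two ratings. The SAP's own timing sentence does not say *only*. The clearest statements are in the Protocol, which is dated 31.05.25, after the SAP of 26.04.24. These points show loose drafting, but they do not produce a day 0 score. The Design sentence names adherence separately from the outcomes, and the specific account in Procedure rules out a baseline rating.

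Two SAP provisions might be offered as a rescue. Imputation from gender, age and baseline data cannot help, because day 0 compliance is observed in nobody and there is nothing to fit. The clause under which "transformations or non-parametric tests will be used where appropriate" deals with violated assumptions, not with an occasion that was never measured.

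The strongest objection is that little follows. The phrase may have been carried over from the appetite sentence (an inference). An analyst with no day 0 column would notice at once, so a misleading estimate is unlikely. That stands, and it is why the point is rated minor.

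It is also fair to say that a one-way test pools the two sites, although controls were randomised only at Bournemouth and instructions were delivered differently there. The planned ANOVA pools sites in the same way, so this is a separate matter.

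**Conclusion.** The point holds. The compliance analysis is wrong as written for all three scales: 3 of the 6 cells are empty, no participant has both scores, and 3 of the 5 effect degrees of freedom cannot be estimated. The day 7 comparison of conditions (2 df) is intact.

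Severity is minor. The primary outcomes and appetite are measured on both days and are unaffected. So are the description of data by group and the checking of adherence ratings against intake records. The optional per-protocol analysis depends on self-reported compliance and not on this ANOVA.

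The conclusion rests on reading the specific timing statements as governing the general Design sentence. It needs no assumption about sample size, effect size or variance.

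**What to change.** Replace the compliance sentence in the SAP's Analyses section with: *For each of the three compliance scales, day 7 scores will be compared between the three conditions (one-way between-groups analysis, or its non-parametric equivalent where assumptions fail).*

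The documents give no unblinding date. If unblinding has not happened, enter this as a dated SAP correction. If it has, report it as a deviation with the reason. The second route may be the only one left, since data collection ended in March 2024 and the Protocol document is a retrospective account from 2025.

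The cost is one sentence and, if needed, a line in the report. No new data are required, and no estimable comparison is given up.

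### The three compliance ratings exist only for day-7 attenders and should be excluded from the SAP's general imputation rule, whose listed predictors omit allocated arm

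*SAP*

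**What the plan says.** **Collection.** The protocol's Adherence section states: "Adherence to the intervention instructions was assessed at the end of the intervention period". The SAP's Compliance section agrees: "Compliance with the intervention instructions will also be assessed at the end of the intervention period". The protocol's Procedure section fixes the visit: "On day 7, participants also completed the adherence questions before the taste perception test". At that same visit "they were asked about any difficulties experienced over the intervention period".

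The other adherence information is not a separate source. The ratings "were verified using records of sweet food consumption over the previous day and verbal reports of difficulties over the intervention week", so that material supports ratings already given. Between visits, the protocol's Intervention/control section describes only a route that the participant must start: "contact details of an additional researcher were also given should questions arise during the course of the study". No exit questionnaire or contact with non-attenders is described.

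**Analysis.** The SAP lists compliance ratings among its outcomes (Data section) and gives them their own ANOVA (Analyses section). It then states that analyses follow intention to treat, "with missing data imputed using models based on gender, age and baseline data". No outcome is exempted, and the text does not say whether imputation is single or multiple. The next sentence reads: "Per-protocol analyses may also be undertaken dependent on participant drop out and self-reported compliance". No compliance threshold is given.

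**The concern.** A participant who does not attend on day 7 has no compliance rating. Read literally, the general rule would supply one. For outcomes measured at both visits, such a model can at least use the participant's own day-0 value. For compliance there is no such value, so the predictors reduce to gender, age and baseline values of other measures.

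The ratings are also specific to the arm by design. Controls were told to carry on eating as they had been, while the other two arms were asked for as large a change as they could manage. A model without arm ignores the main known determinant of these scores. A model without stopping status treats a non-attender like an attender of the same gender, age and baseline.

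Adherence is a named secondary outcome and the trial's main evidence that the diets were followed. If no effect on preference or intake is found, readers will use it to separate an ineffective diet change from one that was not made. Modelled ratings presented as adherence data would weaken that reading.

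**Working it through.** **Inputs from the documents.** Compliance is rated once, on day 7. The predictors are gender, age and baseline data. The planned size is 40 per intervention group, with a final ratio of 2:2:1 (both in the protocol), hence 40, 40 and 20. The figure of 40 can be reached within the stated ranges (a two-sample t-test at 9 mm and SD 14 mm gives 39). It serves here only for weights and a divisor. The documents give no drop-out share and no compliance means, so there is no plan figure for this point to reproduce.

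**Assumptions.** Attender means m are 70 (increase), 65 (decrease) and 90 mm (control). The same share q is missing in each arm: 5%, 10% or 20%. Non-attenders' true mean lies g mm below the attender mean of their own arm, with g = 0 or 40. Gender, age and baseline are taken as balanced across arms, so the average imputed value is the pooled attender mean P.

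**Step 1, pooled mean.** P = (40 × 70 + 40 × 65 + 20 × 90) / 100 = 7200 / 100 = 72 mm.

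**Step 2, bias in an arm's mean after imputation.** Bias = q × [P − (m − g)].

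At q = 10% and g = 0:
- increase: 0.10 × (72 − 70) = +0.2 mm
- decrease: 0.10 × (72 − 65) = +0.7 mm
- control: 0.10 × (72 − 90) = −1.8 mm

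| q | g (mm) | Increase | Decrease | Control |
|---|---|---|---|---|
| 5% | 0 | +0.1 | +0.35 | −0.9 |
| 10% | 0 | +0.2 | +0.7 | −1.8 |
| 20% | 0 | +0.4 | +1.4 | −3.6 |
| 5% | 40 | +2.1 | +2.35 | +1.1 |
| 10% | 40 | +4.2 | +4.7 | +2.2 |
| 20% | 40 | +8.4 | +9.4 | +4.4 |

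**Step 3, effect on a between-arm contrast.** Control minus decrease is 90 − 65 = 25 mm. After imputation at q = 10% and g = 0 it is (90 − 1.8) − (65 + 0.7) = 22.5 mm, a loss of 2.5 mm, which is q × 25. With g = 40 in every arm the loss is the same: 4.7 − 2.2 = 2.5 mm.

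**Step 4, what leaving the ratings unimputed does.** The observed mean differs from the mean over all randomised participants by q × g. With g = 0 this is zero in every arm, so the drift in step 2 disappears. With q = 10% and g = 40 it is +4.0 mm in each arm: the contrast is preserved but the level is still too high. Over q = 5–20% and g = 30–50 mm it runs from 0.05 × 30 = 1.5 to 0.20 × 50 = 10 mm.

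**Step 5, direction.** If the imputed values lie 10 mm below non-attenders' true values, adherence is understated by 0.5, 1 and 2 mm at q = 5%, 10% and 20%.

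**Step 6, precision.** With 40 randomised and 10% missing, 36 ratings exist. If 40 values are counted as observed, the change of divisor alone scales the standard error by √(36/40) = 0.949, about 5% too small. Proper multiple imputation would avoid this, but the SAP does not specify it.

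**The case against.** The strongest reply is that the SAP never says compliance will be imputed. A rule built on baseline data fits the two-visit outcomes more naturally than a rating taken once. That is a fair reading, and it makes this partly an ambiguity. But compliance is a listed outcome, the rule has no exception, and the same section gives compliance a day-0 level in its ANOVA although no day-0 rating is collected. General rules appear to have been carried over to compliance without adjustment, so the literal reading cannot be dismissed.

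Three stronger readings are tempting, and the documents do not support them.

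- A reader might infer that those who stop early are never asked. Anyone who abandons the diet but attends on day 7 is asked about both adherence and difficulties. The gap concerns non-attenders only.
- A reader might infer that adherence is necessarily overstated. That requires non-attenders to have adhered worse than their imputed values, and the documents give neither drop-out nor adherence figures. Because arm is not a listed predictor, imputation could even lower one arm's mean.
- A reader might infer that imputed scores would place drop-outs in the per-protocol set. The SAP names drop-out as a separate consideration, and an imputed score is not self-reported. No written rule settles membership, however, so one is still needed.

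It is also true that observed means do not remove the bias from non-attendance (step 4). The gain from leaving the ratings unimputed is narrower: no drift across arms, no overstated precision and a visible n.

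**Conclusion.** The point holds as a gap in the SAP. Followed literally, the general rule fills in three arm-specific ratings that have no baseline value, using predictors that include neither arm nor stopping status.

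Under the assumed means and 10% missing, the drift attributable to omitting arm is +0.2, +0.7 and −1.8 mm (increase, decrease, control), and the control–decrease contrast shrinks by 2.5 of 25 mm. If non-attenders also score 40 mm lower, the arm biases are +4.2, +4.7 and +2.2 mm, of which 4.0 mm in each arm would remain in observed means. Size and direction rest on the assumed means, missing share and gap. If everyone attends day 7, the problem disappears.

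The matter affects a secondary outcome and any per-protocol analysis. No effect on the primary outcomes is shown. It deserves correction because the remedy is cheap and the ratings are needed to interpret the main result.

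**What to change.** Amend the SAP's Analyses section to state that:

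1. the three compliance ratings are excluded from imputation;
2. observed day-7 ratings are compared by arm, with n for each arm. This also removes the day-0 level from the compliance ANOVA;
3. day-7 non-attendance, with any known reasons, is tabulated by arm beside the compliance results, with a statement that the observed means describe attenders only;
4. any per-protocol set is based on observed ratings and excludes day-7 non-attenders.

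Imputation of the other outcomes is not altered. Contacting non-attenders is not proposed, because the protocol dates the end of data collection to March 2024, before the SAP's date of 26.04.24.

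The cost is a few sentences and one table. The downside is a smaller n for compliance, and the observed means will still not represent those who did not attend.

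### The imputation rule leaves out randomised condition, so imputed day-7 values pull the arms together and bias the condition-by-time contrast

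*SAP*

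**What the plan says.** The last part of the SAP's Analyses section states: "Analyses will be undertaken on an intention-to-treat basis", with "missing data imputed using models based on gender, age and baseline data". It gives no further detail: nothing on condition, on imputing within arm, on single or multiple imputation, or on a sensitivity analysis for missing data. The only other relevant sentence is optional: "Per-protocol analyses may also be undertaken dependent on participant drop out and self-reported compliance". The Protocol has no missing-data rule and no dropout allowance.

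The tests that will use the imputed data compare conditions over time. Pleasantness and desire to eat, both primary in the Protocol (Outcomes), have condition as the first factor, crossed as "x 2 time (day 0, day 7) x 2 food type (sweet foods, non-sweet foods) repeated-measures ANOVAs". Sweet food intake, also primary, has a condition-by-time ANOVA.

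**The concern.** An imputation model should contain every factor that the analysis then tests. Here the named predictors leave out condition. Two participants with the same sex, age and day-0 values would receive the same expected day-7 value whether they were told to eat more sweet food, less, or to change nothing. The imputed records then carry the average effect over all arms, and adding them to the observed records dilutes any real difference.

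The dilution is toward no difference only when missingness is similar across arms. When it is unequal, the arm with more missing data is pulled harder toward the overall mean, and a pairwise contrast can move in either direction. Unequal missingness is plausible here, though not shown. Participants given a dietary change were asked to make it large while controls changed nothing (Protocol, Intervention/control), and controls were recruited only at the second site (Protocol, Procedure).

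**Working it through.** **Inputs from the documents.** Forty per intervention group, an effect of 6–9 mm and an SD of 13–17 mm (Protocol, Participants); final ratio 2:2:1 (Protocol, Procedure). This gives assumed arms of 40 increase, 40 decrease and 20 control.

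The stated 40 can be reproduced from those ranges. With n = 2(1.96 + 0.842)² × SD²/difference², 9 mm with SD 14 gives 38 per group and 8 mm with SD 13 gives 42. The full ranges run from 33 (9 mm, SD 13) to 127 (6 mm, SD 17). The point below does not depend on which pairing was used.

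**Assumptions.** Missing day-7 share of 5, 10 or 20%, missing completely at random within arm; true increase-versus-decrease difference 7.5 mm with control midway; SD of change 15 mm; day 0–day 7 correlation 0.6.

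**Formula.** Let arm k have true mean change μ_k, size n_k and missing share m_k. Without condition in the model, the expected arm mean after imputation is

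(1 − m_k)·μ_k + m_k·M, where M = Σ n_j(1 − m_j)μ_j / Σ n_j(1 − m_j).

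**Equal missingness.** M cancels and the contrast becomes (1 − m) × truth: 0.95 × 7.5 = 7.1, 0.90 × 7.5 = 6.75, 0.80 × 7.5 = 6.0 mm. Simulation of 4,000 trials per scenario (Monte Carlo SE about 0.05 mm) agrees:

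| Missing | Formula | Simulated, no condition | Simulated, complete case |
|---|---|---|---|
| 5% | 7.1 | 7.15 | 7.53 |
| 10% | 6.75 | 6.78 | 7.52 |
| 20% | 6.0 | 5.92 | 7.43 |

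**Unequal missingness.**
- 20% missing in decrease, 5% elsewhere (μ = 3.75, −3.75, 0 for increase, decrease, control; observed n = 38, 32, 19). M = (38 × 3.75 − 32 × 3.75)/89 = 0.25. Increase: 0.95 × 3.75 + 0.05 × 0.25 = 3.58. Decrease: 0.80 × (−3.75) + 0.20 × 0.25 = −2.95. The difference is 6.5 mm against a true 7.5.
- 20% missing in control, 5% elsewhere, decrease 7.5 mm below increase (observed n = 38, 38, 16). If increase and control are truly equal (both 0), M = −285/92 = −3.10 and the increase-minus-control difference is (0.05 − 0.20) × (−3.10) = 0.46 mm. If the true difference is 1.0 mm, M = −301/92 = −3.27. Increase is 0.05 × (−3.27) = −0.16 and control is −0.80 + 0.20 × (−3.27) = −1.45, a difference of 1.29 mm.

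**Other assumptions, same pattern.** With a 9 mm effect in the increase arm only and correlation 0.5, the formula gives 8.55, 8.10 and 7.20 mm. Simulation gives 8.55–8.64, 8.04–8.19 and 7.16–7.20, with complete cases at 9.01–9.15. With 10/20/5% missing (increase/decrease/control), M = 36 × 9/87 = 3.72, and a false decrease-minus-control difference of (0.20 − 0.05) × 3.72 = 0.56 mm appears (simulated about 0.5).

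**Power for the pairwise increase-versus-decrease test, true 7.5 mm (Monte Carlo SE 0.008).**

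| Method | 5% | 10% | 20% |
|---|---|---|---|
| Complete case | 0.58 | 0.57 | 0.50 |
| No condition, deterministic | 0.58 | 0.56 | 0.48 |
| No condition, single stochastic | 0.55 | 0.52 | 0.40 |
| No condition, multiple | 0.53 | 0.48 | 0.32 |
| With condition, multiple | 0.58 | 0.57 | 0.51 |

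A repeat run at 20% gave 0.32 and 0.48 for the last two rows.

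**No true difference in any arm.** Under the 9 mm scenario's other settings, imputation without condition shows no material bias (within about 0.2 mm of zero). Its type I error is 0.05–0.06 for single fill-in and 0.03–0.04 for multiple imputation.

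**Adding condition but keeping a single fill-in.** The bias goes, but pairwise type I error is 0.06, 0.07–0.08 and 0.09–0.11 at 5, 10 and 20% missing (three-arm F test at 20%: 0.11–0.13). Multiple imputation with condition gives 0.05 at each pairwise rate.

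**The case against.** **The sentence may be shorthand.** The time of randomisation is not given, and baseline data could loosely include allocation. What stands is that the intention is unknown. The text favours the literal reading, however. The Protocol (Design) uses baseline for the day-0 assessment, the dietary instructions were handed out only after day-0 measurement was complete (Procedure), and the SAP uses condition as a separate term in every model. If condition was meant, the sentence still needs to say so.

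**The size may be small.** With two visits a week apart, few day-7 values may be missing. This stands: at 5% the loss is about 0.4 mm of 7.5, and the power loss ranges from none to 0.05 depending on the imputation variant.

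**The power figures are not for the planned tests.** They are pairwise, while the SAP plans three-arm ANOVAs, with food type added for taste. This also stands. The proportional shrinkage carries over to those tests; the power values do not.

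**The remedy needs more detail.** Rubin's rules do not say how to pool an ANOVA F test, the three-arm test was not simulated under multiple imputation, and compliance has no day-0 value. These points affect wording, not the finding. With two time points, condition by time is a test on change scores, so it can be pooled as regression contrasts in Stata, which the SAP names.

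**Complete case would also do.** It is unbiased if data are missing completely at random, with almost the same power as multiple imputation with condition. That is fair, but the SAP commits to imputation, and correcting the model is the smaller change.

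**Conclusion.** The concern holds. As written, the rule omits the factor under test and biases the condition-by-time contrast whenever day-7 data are missing and the arms truly differ. With equal missingness the contrast shrinks by about the missing fraction, here about 0.4, 0.75 and 1.5 mm of 7.5 mm at 5, 10 and 20%. With unequal missingness the bias can go either way, and in the examples above a true zero becomes about 0.5 mm when the third arm differs.

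The size rests on missing rates that the documents do not give and on the assumed 40/40/20 arms and effect. The proportional shrinkage does not depend on the SD or correlation; the power figures do. With no missing day-7 data there is no problem. This should be corrected, but it does not by itself invalidate the trial.

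**What to change.** Replace the missing-data sentence in the SAP (Analyses) with:

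> Analyses will be by intention to treat. Missing outcomes will be multiply imputed and combined by Rubin's rules, with condition (or imputation separately by condition), age, gender and day-0 values of the outcome in the imputation model. A complete-case analysis will be reported as a sensitivity analysis, with the number missing per arm.

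State the number of imputations, that condition-by-time effects will be pooled as regression contrasts on change scores, and that compliance is imputed without a day-0 value of its own. Site is an optional addition to the model. Condition as a covariate is preferable to imputing separately by condition, which is less stable in the smaller control arm. Both changes are needed: condition alone with a single fill-in removes the bias but inflates type I error.

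The cost is essentially one sentence and slightly more analysis work. Data collection ended in March 2024 (Protocol, Procedure), so the analysis may already have been run. If so, re-run it under this rule and report both results, so that readers can see whether the rule mattered.
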